5. SUBJECT RECRUITMENT METHODS AND PRIVACY

Subjects are recruited primarily through formal advertisement (i.e., regular newspaper advertisements placed generally in free newspapers), local flyers posted in public areas (e.g., bars, restaurants, stores) and by word-of-mouth. These advertisements are approved under our screening protocol (IRB # 03-0509). Subjects make initial contact by phone with one of our recruiters who have completed the research training and HIPAA compliance web-based modules. If the subject self-discloses information that would make him/her potentially eligible for the study, they will be invited to a screening appointment. Screening is completed by one of our research assistants at the UK Laboratory of Human Behavioral Pharmacology (LHBP). Study investigators may interact with subjects in this setting and appropriate cautions are in place to ensure privacy during the intake process.

6. INFORMED CONSENT PROCESS

All potential subjects that are identified using the subject recruitment methods noted above will provide informed consent prior to participating in the protocol. Subjects that meet the eligibility criteria noted above will come to the LHBP and will undergo a field sobriety test and provide an expired air sample that will be tested for the presence of alcohol. If the subject passes the field sobriety test (walk and turn, one-leg balance [timed], finger-to-nose and backwards-counting tasks) and the expired air sample is negative, he or she will then be given a copy of the approved informed consent document to read and sign. After reading the consent document, the PI or one of the Co-Is on this protocol will address any questions the subject may have in order to assess the subject’s understanding of the protocol. After this, the subject will receive a copy of the informed consent document and will sign a form indicating that they have received a copy of the form they read and signed.

7. RESEARCH PROCEDURES

Subjects that meet the inclusion criteria will participate as outpatients at the LHBP and as inpatients at the Clinical Services Core (CSC) unit of the University of Kentucky Medical Center.

Twenty-five (≈8 women) non-treatment-seeking subjects with AUD will complete the study. Subjects, recruited from the community, will earn \$40/session and a \$40/session completion bonus if they finish the protocol. To maximize medication adherence, a contingency management approach will be used wherein subjects will receive a monetary bonus each day that medications are administered per protocol as verified by Wisepill®. Payments will start at \$5 and increase by \$2 each consecutive day of dosing adherence.

The study protocol will use previously developed methods that have predictive validity for AUD treatment efficacy (Drobles et al., 2003; Hendershot et al., 2016; O’Malley et al., 2002). More specifically, the sensitivity of this clinical laboratory approach was established with a medication already known to be effective for AUD (i.e., naltrexone; see above). After screening, subjects will complete the protocol as outlined in Table 1. After completing the protocol, all subjects will be offered referral to a treatment program per the NIAAA National Advisory Council guidelines (National Council on Alcohol, 1988; Sinha et al., 1999).

Day	Table 1: Protocol Schedule
0	Practice Session at the Laboratory of Human Behavioral Pharmacology (LHBP). Matches Experimental Session, except no ALC administered, nor is there an overnight stay at the CSC. Subjects will receive NAC doses for take-home administration.
1-5	NAC (0, 0.6 or 1.2 g/dose; dose order randomly assigned) administered at 0700 and 1900h.
5	Experimental Session 1 at Inpatient Clinical Services Core (CSC) unit.
6-12	Washout.
13-17	NAC (0, 0.6 or 1.2 g/dose; dose order randomly assigned) administered at 0700 and 1900h.
17	Experimental Session 2 at Inpatient CSC unit.
18-24	Washout.
25-29	NAC (0, 0.6 or 1.2 g/dose; dose order randomly assigned) administered at 0700 and 1900h.
29	Experimental Session 3 at Inpatient CSC unit.
30	Subject discharged from study.

Subjects will be instructed to maintain their standard diet, ALC and cigarette intake throughout participation, with the exception that they will be asked to abstain from ALC for at least 12h prior to a session. All subjects will provide urine and expired-breath samples prior to experimental sessions. The presence of drugs of abuse in the urine or positive BALs upon arrival for experimental sessions will result in rescheduling of the session. Repeated occurrences will result in study dismissal. Subjects will not be allowed to smoke tobacco cigarettes during experimental sessions, consistent with previous work (O’Malley et al., 2002).

NAC Maintenance Conditions. After completing screening, a subject will be randomized to a NAC dose order condition using a random number generator. Completing subjects will experience all dose conditions. A pharmacist in the Investigational Drug Service will maintain the randomization key to preserve the double blind. NAC doses will be prepared with commercially available drug placed into opaque capsules. Cornstarch will be used as filler. Placebo capsules will contain only cornstarch, but will be visually identical to capsules that contain NAC. Placebo capsules will also be washed in a NAC slurry to control for the

Behavioral Effects of Drugs: Inpatient (34) (Alcohol and N-Acetylcysteine) (PI: [name].)

distinct smell of NAC as has been done in previous research ([name]., Personal Communication). Subjects will receive practice taking the study capsules during the practice session. Subjects will be provided two placebo capsules during this session and instructed on how to correctly administer those capsules. Subjects will be told that these capsules are placebos, but that placebo and NAC capsules will look visually identical.

Total daily doses are 0, 1.2 and 2.4 g/day (i.e., 0, 0.6g and 1.2 g administered two times daily at 0700 and 1900h; Table 1). One of the doses reduced ALC use in one study (i.e., 1.2 g/day; Squeglia et al., 2016) and the other dose reduced elevated brain glutamate levels in another (i.e., 2.4 g/day; Schmaal et al., 2012). Testing two doses in this study will inform dose selection when NAC is advanced to a clinical trial. The dosing regimen and maintenance period were chosen based on previous studies (Amen et al., 2011; LaRowe et al., 2013; Squeglia et al., 2016).

1975-2300h	Recreational activities (i.e., movies, magazines, and books).
2300h	Lights out.
0700h	Subject provided a standardized breakfast.
0730-0800h	BAL sample and field sobriety test.
0800h	Discharged from CSC and car keys returned.

Session Activities. On experimental session days, subjects will arrive at the LHBP at the University of Kentucky at 1400h. Upon arrival to the LHBP, the LHBP staff will take the subject's car keys and will return them when the subject is released from the hospital the following morning. Should the subject leave the hospital prior to that time, the LHBP staff or subject will arrange transportation (e.g., arrange a taxi). The car keys will be returned the morning following the experimental session upon successful completion of a field sobriety test.

Behavioral Effects of Drugs: Inpatient (34) (Alcohol and N-Acetylcysteine) (PI: [name].)

Urine and expired breath samples will be obtained for drug and ALC testing. A field sobriety test will be completed. Time of maintenance dosing will be confirmed by self-report and Wisepill® log. If subjects miss more than 3 doses or take doses more than 2 hours outside their scheduled window on 3 occasions within a single dose condition, they will be coached on adherence and that dose condition will be repeated. If this non-adherence occurs again during any other dose condition (or during the repeat condition), the subject will be dropped from the study. Subjects will report their ALC consumption during each 4-day maintenance block using the TLFB (Sobell et al., 1992). Subjects will be then admitted to the CSC at 1500h for their overnight stay and provided a light snack upon admission.

ALC Self-Administration Procedures. The reinforcing effects of ALC, alone and during maintenance on NAC will be assessed using a sophisticated clinical laboratory approach that has predictive validity for AUD pharmacotherapy efficacy (Drobes et al., 2003; Hendershot et al., 2016; O'Malley et al., 2002). The primary outcome measure for this procedure is Number of Drinks Chosen. Testing under this procedure involves two phases: 1) Sampling and 2) Self-Administration.

Sampling Phase. Subjects will complete a Sampling Phase at 1600h during experimental sessions to acquaint them with ALC effects. During each Sampling Phase, subjects will receive a single administration of 95% ALC mixed with non-alcoholic mixer (e.g., lemon lime soda, tonic water) (designed to raise BALs to 0.03 g/dl), to be consumed over 5 minutes.

Self-Administration Phase. After sampling the ALC dose, subjects will complete the Self-Administration Phase. During each Self-Administration Phase, subjects will complete 2 1-h choice blocks in which they will be provided with a tray containing 4 drinks, with each drink prepared with 95% ALC mixed with non-alcoholic mixer (e.g., lemon lime soda, tonic water) (designed to raise BALs 0.015 g/dl/drink) and a “tab” detailing the cost of each drink, based on the cost of a drink purchased in a local bar (i.e., \$3.00). Subjects will be instructed to consume as many drinks on the tray as they want during the 1-h choice block. Subjects may instead choose to receive the corresponding dollar amount for the drinks that they do not consume. At the end of the first choice block, the drink tray will be replaced with a second tray of 4 drinks for the second choice block. Subjects can thus consume a maximum of 8 drinks or earn maximum of \$24, but may choose freely between these two options. Including money as an alternative reinforcer provides an incentive for not drinking ALC, which models the natural ecology. Any money earned will be added to that subject's \$40 payment for attending the session.

Subjective-Effects Questionnaires. Five standardized subjective-effects questionnaires that measure various aspects of mood and ALC effects (Ray et al., 2009; Roche et al., 2016) will be completed as outlined in Table 2: 1) ALC Urge Questionnaire to measure craving (Bohn et al., 1995); 2) Subjective High Assessment Scale (Schuckit, 1984); 3) Biphasic ALC Effects Scale (Martin et al., 1993); 4) Profile of Mood States (Schacham, 1983) and 5) Drug Effects Questionnaire (Johanson and Uhlenhuth, 1980).

Safety and Tolerability Measures. Physiological measures (i.e., BAL measurements, heart rate and blood pressure) will be recorded upon arrival at the LHBP, before ALC administration and throughout the session at the intervals noted in Table 2 using digital monitors. ALC will not be administered if a subject's heart rate is ≥ 100 bpm, systolic pressure is ≥ 150 mmHg or diastolic pressure is ≥ 100 mmHg. A subject will be excluded from further participation if he/she exhibits hypersensitivity (i.e., heart rate > 130 bpm, systolic pressure > 180 mmHg, diastolic pressure > 120 mmHg) during maintenance on NAC and/or to the effects of ALC. The UKU Side Effects Rating Scale will be completed at the end of sessions (Lingjaerde et al., 1987).

Trait Questionnaires and Cognitive Behavioral Tasks. To explore potential mechanisms of NAC effects, subjects will complete a battery of trait measures at screening that assess various aspects of personality, including the Zuckerman-Kuhlman Personality Questionnaire, the Barratt Impulsiveness Scale and the Snaith-Hamilton Pleasure Scale (Patton et al., 1995; Snaith et al., 1995; Zuckerman and Kuhlman, 2000). As outlined in Table 2, subjects will also complete the Commodity Purchase Task, n-back Task, the Go/Stop Task and Money and Alcohol and Money Delay Discounting Tasks. These specific tasks measure several key facets of alcohol-related decision-making and impulsivity (MacKillop, 2016; Reynolds et al., 2008) and, along with the self-administration and subjective effects outcomes described above, model key stages of the addiction cycle (Litten et al., 2016b; MacKillop, 2016).

Commodity Purchase Tasks (Appendix A). Commodity tasks will be used to assess economic demand for alcohol and soda (Amlung et al., 2015; Bruner and Johnson, 2014; Murphy and MacKillop, 2006; Strickland and [name], 2017). In these task subjects are asked to indicate the hypothetical number of items

Behavioral Effects of Drugs: Inpatient (34) (Alcohol and N-Acetylcysteine) (PI: [name].) (e.g., one alcoholic drink) they would purchase at a range of monetary increments (e.g., \$0.00 [free] to \$15/drink). All choices are hypothetical and will not be purchased or administered. Data from the commodity purchase task will be analyzed using economic demand equations previously applied to purchase task data (e.g., Strickland et al., 2016). Primary outcomes of this task include elasticity of demand (α) and intensity of demand (Q_0).

n-Back (Appendix B). The n-Back task will be used to measure working memory and working memory capacity (Jaeggi et al. 2010). In this task, subjects are presented with a sequence of numbers and asked to indicate when the current stimulus matches the one from “n” steps earlier. Two settings will be used in this study, the 1-back and the 2-back (i.e., matching 1 and 2 stimuli back, respectively). The primary outcome of this task is the percentage of correct responses.

Go/Stop Task (Appendix C). A cued go/stop task will be used as a measure of response-inhibition (Miller et al., 1991). In this task, subjects must respond to target stimuli and withhold responses to non-target stimuli. During this task, go stimuli (e.g., a horizontal rectangle) will be followed by go target stimuli (i.e., a green horizontal rectangle) 80% of the time and followed by no-go stimuli (i.e., a blue horizontal rectangle) 20% of the time. Conversely, no-go stimuli (e.g., a vertical rectangle) will be followed by no-go target stimuli (i.e., a blue vertical rectangle) 80% of the time and go target stimuli (i.e., a green vertical rectangle) 20% of the time.

Hypothetical Delay Discounting (Appendix D). A 5-trial adjusting delay discounting task will be used to rapidly assess discounting rates for various commodities (Koffarnus and Bickel, 2014). In this task, subjects making a series of 5 choices between an immediately available, smaller reinforcer and a larger reinforcer at various delays. Versions of this task with monetary (e.g., \$1000 delayed versus \$500 now) and alcohol (e.g., \$1000 of alcohol delayed versus \$500 of alcohol now) commodities will be used. Subjects will be told that all choices are hypothetical. The primary outcome of this task is the discounting rate (k). Previous research has demonstrated that this measure provides rapid and accurate discounting rates across a range of commodities (Cox and Dallery, 2016; Koffarnus and Bickel, 2014; Strickland et al., 2017).

Data Analysis

Data will be analyzed as raw scores. Statistical significance refers to $p < .05$. Number of Drinks Chosen on the ALC self-administration procedure will be analyzed with a one-factor, repeated-measure ANOVA with NAC dose (0, 1.2 and 2.4 g/day) as the factor. A significant attenuation (i.e., decreased ALC self-administration) will be inferred if the main effect of NAC attains statistical significance in the ANOVA. Tukey’s HSD *post-hoc* test will be used to make appropriate pair-wise comparisons between means if the ANOVA outcome attains statistical significance. Data from the subjective-effects questionnaires and safety/tolerability measures following administration of the sampling dose will be calculated as peak effect (i.e., the maximum score observed after ALC sampling). These data will be analyzed in the same fashion as ALC self-administration data. The influence of relevant biological (e.g., age) and behavioral variables (e.g., cigarette smoking, weekly ALC use) will be determined in initial correlation analyses and included as covariates in analyses should they be significantly associated with outcomes. Outcomes from trait questionnaires and cognitive behavioral tasks will also be correlated with self-administration, subjective effect and physiological data to explore the mechanisms by which NAC attenuates the effects of ALC.

Power and Sample Size Considerations. We used the results of a prior meta-analysis of human laboratory studies of ALC self-administration and craving to determine an appropriate sample size for the present experiment (Hendershot et al., 2016). That meta-analysis demonstrated that naltrexone maintenance decreased the quantity of ALC consumed and self-reported craving relative to placebo with an average estimated effect size (i.e., Cohen’s f) of approximately 0.27. Considering the overall design and use of three NAC doses, enrolling 25 subjects will provide sufficient power (power = 0.80, $\alpha = 0.05$, G*Power) to detect a medium effect size (f) of approximately 0.26 for attenuation of the effects of ALC as a function of NAC dose.

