17. DATA AND SAFETY MONITORING

Data Monitoring Plan. Data will be collected using a computerized data collection and management system. This system automates the collection of the subjective-effect and physiological data, which ensures the accuracy and completeness of data collection. The data are stored in a unique file on the hard drive of the computer and are printed after all the tasks are completed. Paper-and-pencil task data are verified by staff and double-entered into excel spreadsheets after each session. In all instances, the data files do not contain the name of the subject; but instead, a unique four-digit number identifies each subject. A computer file linking the unique number with the subject's name will be kept on a stand-alone, password-protected computer. Data files for experimental tasks and physiological measures from each experimental session will be manipulated and combined into a single electronic spreadsheet for each subject by the PI. Data for all subjects will then be combined into a single electronic spreadsheet and separated by experimental measure for statistical analysis using SPSS (IBM Corporation, Armonk, NY).

The primary outcome for this study will be Number of Drinks during ALC self-administration. Secondary outcome measures will include craving, BALs, physiological and subjective response to ALC, self-reported ALC use in the natural environment during maintenance, as well as performance on cognitive-behavioral tasks, and the Udvalg for Kliniske Undersøgelser (UKU) Side Effects Rating Scale.

As noted above, the majority of data are collected using an automated computer system, which increases the accuracy and completeness of data collection and ensures the validity and integrity of the data. Hand written questionnaires and tasks are double-entered and verified by staff prior to analysis. The initial data manipulation described above will be conducted twice and compared. The quality of manipulated data and data analyses will be monitored by random inspection by the PI and/or Co-Investigators.

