Appendix D

5-Trial Adjusting Delay Discounting Task (Table from Koffarnus and Bickel 2014)

The below table describes the outcomes for the 5-trial task. For each of the 5 choices (i.e., No.), the subject is asked if they would prefer the immediate or delayed reinforcer. The delay to the delayed choice is systematically increased or decreased based on previous trial choice (i.e., Delay Choice; increases if delay is chosen, decreases if immediate is chosen). The primary outcome is k as labeled in the table below.

Table 1
Parameters of the Possible Individual Choice Trials in the 5-Trial Adjusting Delay Task

Index	Delay choice	No.	ED ₅₀ (days) if last choice is:		k if last choice is:	
			Immediate	Delayed	Immediate	Delayed
1	1 hr	5	0.04167	0.05893	24.0	17.0
2	2 hr	4				
3	3 hr	5	0.1021	0.1444	9.79	6.93
4	4 hr	3				
5	6 hr	5	0.2041	0.3062	4.90	3.27
6	9 hr	4				
7	12 hr	5	0.4330	0.7071	2.31	1.41
8	1 day	2				
9	1.5 days	5	1.225	1.732	0.816	0.577
10	2 days	4				
11	3 days	5	2.450	3.464	0.408	0.289
12	4 days	3				
13	1 week	5	5.292	8.573	0.189	0.117
14	1.5 weeks	4				
15	2 weeks	5	12.12	17.15	0.0825	0.0583
16	3 weeks	1				
17	1 month	5	25.28	43.05	0.0396	0.0232
18	2 months	4				
19	3 months	5	74.56	105.4	0.0134	0.00949
20	4 months	3				
21	6 months	5	149.1	210.9	0.00671	0.004741
22	8 months	4				
23	1 year	5	298.2	516.5	0.00335	0.00194
24	2 years	2				
25	3 years	5	894.7	1265.	0.00112	0.000791
26	4 years	4				
27	5 years	5	1633.	2310.	0.000612	0.000433
28	8 years	3				
29	12 years	5	3579.	5368.	0.000279	0.000186
30	18 years	4				
31	25 years	5	7748.	9131.	0.000129	0.000110

Note. ED₅₀ = Effective Delay 50%.

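### The rule to analyse raw scores, read literally, puts the discounting rate k on a poor scale; analysing ln(k) would recover power at the cost of one sentence

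*Combined protocol and SAP*

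**What the plan says.** Section 7, Data Analysis, opens with "Data will be analyzed as raw scores" and sets significance at 0.05. It gives no transformation, rank method or distribution check for any outcome.

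The delay discounting paragraph of section 7 names the rate k as the outcome, for a money version and an alcohol version. Appendix D repeats this: "The primary outcome is k as labeled in the table below". Its table gives 32 values of k, the largest 24.0 and the smallest 0.000110.

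On the tests to be used:

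- For the cognitive-behavioral tasks the plan names correlation only: "Outcomes from trait questionnaires and cognitive behavioral tasks will also be correlated with self-administration, subjective effect and physiological data". It does not name the coefficient.
- The repeated-measures ANOVA is written for Number of Drinks Chosen. It is extended to peak subjective-effect and safety scores by "These data will be analyzed in the same fashion as ALC self-administration data". That sentence does not reach the cognitive tasks.

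Section 17 counts among the secondary outcomes "as well as performance on cognitive-behavioral tasks". Section 1 calls the related third aim exploratory. No mean, SD or expected effect for k is given anywhere.

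**The concern.** A score whose possible values are spaced by ratios rather than by differences suits least-squares methods on the log scale, not the raw scale. On the raw scale a few steep discounters supply most of the variance, and differences among the other subjects hardly count. An analyst who follows the general rule to the letter would run the planned correlations on such a score. With 25 subjects, a real association between discounting and drinking, or a real effect of NAC on discounting, could then be missed because of the scale chosen. Because the rule is written down, this is more than a missing detail.

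**Working it through.** **1. The plan's own power figure.** Inputs from section 7: f = 0.26, N = 25, m = 3 conditions, alpha 0.05. Within-subject correlation ρ = 0.5 and sphericity are assumed, since the documents give neither. λ = f²·N·m/(1 − ρ) = 0.0676 × 25 × 3 / 0.5 = 10.14, on 2 and 48 degrees of freedom. The noncentral F gives power 0.795, against 0.80 stated. The figure is reproduced, but it is stated for the effects of ALC and not for k. It serves here only as a benchmark.

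**2. The scale of k (Appendix D).** The range is 24.0 / 0.000110 = 218,182-fold, which is ln(218,182) = 12.29 log units. Over 31 steps that averages 12.29 / 31 = 0.40 per step. Ratios of neighbouring values lie between about 1.17 (0.000129 / 0.000110) and 1.74 (17.0 / 9.79), so the steps are roughly even in logs. On the raw scale they are not. The top step is 24.0 − 17.0 = 7.0, and a middle step is 0.0396 − 0.0232 = 0.0164, so the first counts 7.0 / 0.0164 ≈ 427 times as much.

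**3. Correlation, the analysis the plan names.** Simulation with N = 25, ln(k) normal and rounded to the tabulated values, median k of 0.005, 0.02 or 0.1, and a true correlation of 0.5 with ln(k). The SD of ln(k) is assumed. Share lost = 1 − raw power / log power.

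| SD of ln(k) | Pearson power on ln(k) | Pearson power on raw k | Share lost |
|---|---|---|---|
| 1 | 0.74 | 0.59 | 20% |
| 1.5 | about 0.75 | 0.48 | 36% |
| 2 | about 0.75 | 0.40 | 47% |
| 2.5 | about 0.75 | 0.34–0.37 | 51–55% |

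A second set of runs used a true correlation of 0.53, chosen to give about 80% power on ln(k), and a wider range of SDs. At SD 0.5 power was 0.77–0.79 on ln(k) and 0.72–0.74 on raw k, a loss of 6–7%. At SD 3 the loss was 49–57%. A Spearman correlation kept 0.72–0.75 in every setting, and it is the same on k as on ln(k).

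At SD 2, the most extreme of the 25 subjects carries a median of 65–67% of the raw sum of squares.

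**4. ANOVA across doses, conditional because the plan does not state it for k.** Both NAC doses shifted by 0.54 SD on ln(k), ρ = 0.5:

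| SD of ln(k) | ANOVA power on ln(k) | ANOVA power on raw k | Share lost |
|---|---|---|---|
| 1 | 0.76 | 0.52–0.53 | 30–32% |
| 1.5 | 0.76–0.78 | 0.34 | about 56% |
| 2 | 0.76–0.78 | 0.21–0.22 | about 71–73% |
| 2.5 | 0.76–0.78 | 0.13–0.18 | about 77–83% |

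The last three shares use 0.77 for the log scale. At ρ = 0.7 the same shift gives 0.93–0.95 on ln(k), against 0.47–0.48, 0.30–0.31 and 0.19–0.23 on raw k at SD 1.5, 2 and 2.5. The loss at SD 1.5 is then about half (1 − 0.475 / 0.94 = 0.49).

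With the effect sized for a nominal 80% power on ln(k), and ρ = 0.5 or 0.8, the loss was 7–17% at SD 0.5, 30–43% at SD 1, 54–68% at SD 1.5 and 71–83% at SD 2. With no true effect, raw k was rejected in about 0.01–0.03 of trials at SD 1.5 or more, so the test errs on the conservative side.

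**The case against.** A reader might infer that, because k spans a 218,000-fold range, most of the power for this outcome is lost. The documents do not support that. The range is what the instrument can return, not the spread to be expected among 25 subjects. The loss depends on the SD of ln(k), which is not given, and at SD 0.5 it is small. The largest losses belong to a dose ANOVA that the plan does not specify for k. For the correlation it does specify, half the power is reached only at an SD of about 2.5 to 3.

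The rule may also be meant less literally. The plan itself reduces data to peak effects and fits demand equations to the purchase task, and k is already a derived parameter. Raw scores could therefore mean not changed from baseline. The coefficient is unnamed too; if it is a rank coefficient, taking logs changes nothing.

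These points limit the size of the concern but do not remove it. No sentence exempts k, none mentions ranks, and both places that define the outcome name k untransformed. Raw k lost power in every setting tried with a Pearson correlation or an ANOVA. An SD as small as 0.5 would confine subjects to a narrow part of the table, since 0.5 / 0.40 is about 1.3 steps out of 31.

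**Conclusion.** The concern holds in limited form, as a cheap improvement. Read literally, the rule puts k on a poor scale. Under an assumed SD of ln(k), a Pearson correlation loses about 20% of its power at SD 1 and about 35–55% at SD 1.5–2.5, but under 10% at SD 0.5. If k is also compared across doses by ANOVA, more than half of a nominal 80% power goes at an SD of about 1.5 or more. These figures rest on a normal ln(k) and, for the correlation, on a Pearson coefficient.

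Neither a threat to the trial's main result nor a risk of false dose claims follows. Discounting falls under a secondary outcome and an exploratory aim, Number of Drinks Chosen and N = 25 are untouched, and the raw-scale dose test would be conservative. The harm is a missed signal about mechanism.

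**What to change.** Add one sentence after the general rule in section 7, Data Analysis: *The discounting rate k is the exception: it will be analyzed as ln(k) in all correlations and in any comparison across NAC doses.* It should cover the money and the alcohol versions. The same edit can name the correlation coefficient and say whether k is to be compared across doses. It is best made before unblinding, so that the scale is not chosen after the results are seen.

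The cost is one sentence and one computed variable per task version. Every tabulated k is above zero, so no constant has to be added. The small downside is that effects are reported as ratios of k. No subjects, visits or procedures are added.
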